6.5.3 Coronary Imaging

Change in coronary artery perivascular fat attenuation index (FAI) measured by CCTA at Week 15 for participants.

6.5.4 Plaque Burden and Characteristics

Change in Noncalcified and low attenuation coronary artery plaque volume, assessed by CCTA at week 15 as compared to Baseline, in active and placebo patients.

Change in total plaque volume, assessed by CCTA at week 15 as compared to Baseline, in active and placebo patients.

7 ADVERSE EVENTS AND SAFETY REPORTING

7.1 Safety and Tolerability Assessments

Safety and tolerability will be assessed on an ongoing basis by review of reported AEs, physical examinations, vital signs (SBP/DBP and heart rate), and clinical safety labs (hematology and serum chemistry).

7.2 Definition of Adverse Event

An AE is any untoward medical occurrence in a subject administered a pharmaceutical product, which does not necessarily have to have a causal relationship with the pharmaceutical product treatment. An AE can, therefore, be any unfavorable and unintended sign, symptom, or disease temporally associated with the use of a medicinal product, whether or not related to the medicinal product. Any worsening of the subject's disease under study or other medical conditions will also be considered to be an AE, unless it is within the normal range of disease fluctuation for that subject. Treatment-emergent adverse events (TEAEs) are defined as any AE that starts or increases in severity after the first randomized dose of study treatment (active or placebo).

Clinically meaningful (for a given subject) changes in physical examination findings and abnormal objective test findings (e.g., laboratory or X-ray) should also be recorded as AEs.

The criteria for determining whether an abnormal objective test finding should be reported as an AE are as follows:

1. Test result is associated with accompanying symptoms or is of clinical concern.
2. Test result requires additional diagnostic testing or medical/surgical intervention.
3. Test result leads to a change in study dosing or discontinuation from the study, significant additional concomitant drug treatment, or other therapy.
4. Test result leads to any of the outcomes included in the definition of a SAE.

Merely repeating an abnormal test, in the absence of any of the above conditions, does not meet condition 2 above for reporting as an AE.

Any abnormal test result that is determined to be an error does not require reporting as an AE.

7.3 Definition of a Serious Adverse Event

A SAE is defined in 21 CFR 312.32(a) as follows:

An AE is considered "serious" if, in the view of either the Investigator or Sponsor, it results in any of the following outcomes:

- Death.
- Life-threatening AE.
- Inpatient hospitalization or prolongation of existing hospitalization.
- Persistent or significant incapacity or substantial disruption of the ability to conduct normal life functions.

- Congenital anomaly/birth defect.

Important medical events that may not result in death, be life-threatening, or require hospitalization may be considered serious when, based upon appropriate medical judgment, they may jeopardize the subject or the subject requires medical or surgical intervention to prevent one of the outcomes listed in this definition. Examples of such medical events include allergic bronchospasm requiring intensive treatment in an emergency room or at home; blood dyscrasias or convulsions that do not result in inpatient hospitalization; or the development of drug dependency or drug abuse.

7.3.1 Life-Threatening Adverse Event

The term “life-threatening” in the definition of “serious” refers to an event in which the subject was at risk of death at the time of the event; but it does not refer to an event that, hypothetically, might have caused death if it were more severe.

7.3.2 Hospitalization

This is defined as the subject being hospitalized overnight, or the subject’s hospital stay being prolonged for at least an additional overnight stay. Preplanned hospital stays or hospital stays for nonmedical social reasons will not be considered as hospitalization. “Twenty-three-hour hospitalizations” for observation should be discussed with the medical monitor to determine whether they are appropriate for SAE reporting.

7.3.3 Pregnancy

Female subjects must be surgically sterile (hysterectomy, bilateral oophorectomy, or bilateral tubal ligation) or if a female subject is of childbearing potential, she must agree to use a medically acceptable highly effective method of contraception during the study and for 90 days after the last dose of study drug to be eligible for participation in the study (see Inclusion Criteria, [Section 4.2](#); and Contraceptive Measures, [Section 5.10.2](#)). All female subjects must have a negative serum pregnancy test at Screening and a negative urine pregnancy test at day 1 prior to dosing to be eligible for the study. A urine pregnancy test will also be performed at the end of study at the post-treatment Follow-up Visit.

7.3.4 Subject Withdrawal

If the subject discontinues study treatment due to an AE and withdraws from the study, the reason for the subject withdrawal is to be recorded as due to a specific AE.

7.4 Eliciting and Reporting of Adverse Events

AE monitoring will start immediately following the first dose at Visit 1 and will continue through the Follow-up Visit. Any subject with a possible study treatment-related AE at the Follow-up Visit will be followed until resolution or stabilization of the event. Further, any SAE, whether related or unrelated to study treatment that occurs within 30 days following the last dose of study treatment will be followed until resolution or stabilization of the event. This may require additional clinical assessments and laboratory tests. The follow-up results will be recorded in the subject's source documentation and in the eCRF.

Subjects will be instructed to report all AEs experienced during the study, and subjects will be assessed in clinic for the occurrence of AEs throughout the study. To avoid bias in eliciting AEs, subjects will be asked general, non-leading questions such as "How are you feeling?"

All AEs, including pretreatment and TEAEs, reported by the subject, observed, or otherwise identified by the Investigator or other Investigational Site personnel will be documented.

Medical conditions existing at Screening should be recorded as medical history. New or worsening pre-existing medical conditions or diseases are considered AEs if they arise or worsen after dosing (Visit 1) and should be recorded as AEs.

Surgical procedures themselves are not AEs; they are therapeutic measures for conditions that require surgery. The condition for which the surgery is required is an AE if it occurs or is detected following the first dose of study treatment at Visit 1 through the Follow-up Visit. Conditions leading to planned surgical procedures are not AEs if the condition(s) was (were) known before study treatment. In the latter case, the condition should be reported as medical history.

7.4.1 Routine Reporting of Adverse Events

All AEs, whether or not associated with study treatment, that are observed by the Investigator, other Investigational Site personnel, or the subject will be recorded in the subject's source documentation and on the AE page of the eCRF. An SAE listing generated based on the eCRF pages will be submitted to the Sponsor at regularly scheduled intervals to allow the Sponsor to meet expedited regulatory reporting requirements under 21 CFR 312.32 and regular regulatory reporting requirements under 21 CFR 312.33.

For each AE, the following information will be entered in the eCRF:

- Medical diagnosis of the event in standard medical terminology (if a medical diagnosis cannot be determined, a description of each sign or symptom characterizing the event).
- Date of onset of any new AE or worsening of a previously observed AE.
- Date of resolution of the event (or confirmation ongoing).
- Whether the event is serious (per definition in [Section 7.3](#)), and if so, the reason it is considered serious.
- Severity of AE (per definition in [Section 7.6](#)).
- Assessment of the causality of the AE to the study treatment (per definition in [Section 7.5](#)).
- Action taken in treating the AE (including concomitant medications or therapies administered) and/or change in the study treatment administration or dose (including whether the study treatment was temporarily interrupted or discontinued).
- Outcome of AE (per definition in [Section 7.7.1](#)).

7.4.2 Reporting of Serious Adverse Events, Including Death

The Sponsor will adhere to all expedited regulatory reporting requirements as per 21 CFR 312.32.

If an SAE, including death occurs during this study or within 30 days following the last dose of the study treatment, the Investigator must notify the Medical Monitor **within 24 hours** after becoming aware of the event.

Initial notification via the telephone does not replace the need for the Investigator to complete and sign the SAE Form within the time frames outlined in the protocol. This timeframe also applies to additional new information (Follow-up) on previously forwarded SAE reports.

Medical Monitor:

[name]
Safety Office, Integrium, LLC
Office: [contact]
Cellular: [contact]
Email: [contact]

SAE Forms will be provided by the Sponsor or Sponsor designated CRO. If all information is not known at the time of initial reporting, an initial report should still be made. In the event there is a question as to whether the experience is serious, the information should be forwarded to the Medical Monitor for review. The Investigator is responsible for following up on completion of the SAE Form. For all SAEs, the Investigator must pursue and provide information to the study Medical Monitor in accordance with the timeframes for reporting specified above. In general, this will include a description of the AE in enough detail to allow for a complete medical assessment of the case and independent determination of possible causality. Information on other possible causes of the event, such as concomitant medications and illnesses, must be provided. In the case of a subject death, a summary of available autopsy findings must be submitted as soon as possible to the Medical Monitor.

In the event of a medical emergency for an SAE that is unexpected (as defined in [Section 7.7](#)) and possibly related to the study treatment(s) (i.e., an adverse reaction or suspected adverse reaction as defined in [Section 7.4](#)), the Investigator in consultation with the Medical Monitor may request that a blind be broken in instances when the knowledge of the assigned treatment may impact the subjects' medical management.

The initial SAE Form and any subsequent Follow-up SAE Forms submitted to provide more accurate, corrected, or new information must be signed by the Investigator. The Investigator and Investigational Site Personnel must make every reasonable effort to obtain, from other institutions if necessary, all supporting medical case records as needed to comply with expedited Investigational New Drug application (IND) safety reporting requirements.

If the SAE involves expedited IND safety reporting (as determined by the Sponsor or designee), all supporting medical records must be submitted to the Sponsor or designee within 4-calendar days for death or life-threatening events, and 10 calendar days for all other events. In cases where medical records and supporting documentation are unobtainable, the Investigator must generate a narrative of the event utilizing, when necessary, interviews with the subject, their family members and care givers as appropriate.

The Investigator must also promptly inform the governing IRB of the SAE in accordance with the governing IRB's requirements. Any SAE that is determined by the Sponsor to be reportable

to the FDA as an IND Safety Report (as defined in 21 CFR 312.32) will be reported to FDA by the Sponsor or designee within the specified time frame. All IND Safety Reports will also be promptly provided to the Investigator for submission to his/her IRB. Similarly, any SAE that is determined by the Sponsor to require expedited reporting to other regulatory authorities will be reported to the appropriate authorities by the Sponsor or designee within the specified time frames and will be provided to the Investigator for submission to his/her IRB.

The SAE report will evaluate the relationship of the adverse experience to study treatment and underlying disease. Based on this assessment, a decision will be made concerning the need for further action. The primary consideration governing further action is whether new findings affect the safety of subjects participating in the clinical trial. If the discovery of a new adverse experience related to the study treatment raises concern over the safety of continued administration of study treatment, the Sponsor will take immediate steps to notify the regulatory authorities.

Further action that may be required includes the following:

1. Alteration of existing research by modification of the protocol.
2. Discontinuation or suspension of the study.
3. Alteration of the informed consent process by modification of the existing consent form and informing current study participants of new findings.
4. Modification of previously identified expected adverse experiences, to include adverse experiences newly identified as study treatment related.

7.4.2.1 Pregnancy Reporting

If the subject or partner of a subject participating in the study becomes pregnant during the study or within 30 days of discontinuing study medication, the Investigator should report the pregnancy to Integrium within 24 hours of being notified. Safety personnel will then forward the Exposure In-Utero form to the Investigator for completion.

The subject or partner should be followed by the Investigator until completion of the pregnancy. If the pregnancy ends for any reason before the anticipated date, the Investigator should notify the Sponsor. At the completion of the pregnancy, the Investigator will document the outcome of the pregnancy. If the outcome of the pregnancy meets the criteria for immediate classification as an SAE (i.e., postpartum complication, spontaneous abortion, stillbirth, neonatal death, or congenital anomaly), the Investigator should follow the procedures for reporting an SAE.

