3.2.1 Screening Period (Day -28 to Day -1)

3.2.1.1 Screening Visit

At Screening, potential subjects will be given a detailed oral presentation describing the nature, purpose, risks, and requirements of the study and will receive detailed written information. Subjects will be given ample time to consider participation and ask questions that will be adequately addressed by site personnel.

Once the subject is satisfied that he/she is willing to participate in the study, he/she will be asked to sign the study informed consent form (ICF) (refer to [Section 11.2.4](#) for further detail regarding the ICF). The Investigational Site personnel obtaining written consent from the subject will also sign the form to confirm consent has been obtained.

Once signed, the Investigator will retain the original ICF for the subject's study records and provide the subject with a signed copy. The Investigator will verify that informed consent has been obtained from each subject prior to enrollment into the study and prior to the subject undergoing any study-related procedures.

Subjects will report to the clinic in the morning following a 10-hour fast. Screening activities after obtaining informed consent will be conducted and consist of the following:

- Review of eligibility criteria.
- Collection of demographic data (sex, date of birth (DOB), race, and ethnicity).
- Completion of medical history, including tobacco and alcohol use.
- Review of prior and concomitant medications and supplements.
- Physical examination will be performed.
- Height and weight will be measured.
- IGA will be performed.
- PASI Score will be evaluated.
- BSA will be measured.
- DLQI questionnaire will be completed.
- Measurement of vital signs (SBP/DBP and heart rate).
- Collection of fasted blood samples for (see [Section 6.3.2](#) for a list of tests):
 - Clinical laboratory tests (including serum pregnancy test for females and activated partial thromboplastin time (aPTT) test).
 - Serology (Hepatitis B and C, and HIV).

- CCTA will be performed.

For subjects who meet eligibility criteria based on the Screening assessments, instruction will be provided on the following:

- Use of adequate contraceptive methods (see [Section 5.10.2](#)) for the duration of the study (Screening through Follow-up Visit (Visit 8));
- Avoid use of concomitant medication unless deemed necessary by the Investigator, and avoid prohibited medications as defined in [Section 5.9.2](#);

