3.2.4 End of Study/Early Termination Visit (EOS/ET Visit)

3.2.4.1 Visit 7 (Week 15, Day 106 ± 3 days)/ ET Visit

Subjects will report to the clinic in the morning following a 10-hour fast where the following activities will be performed:

- Collection of fasted blood samples for (see [Section 6.3.2](#) for a list of tests):
 - Clinical laboratory tests (including urine pregnancy test for females, biomarkers test, and aPTT test).
 - Immunogenicity testing.
- Review of concomitant medications and supplements.
- Physical examination will be performed.
- IGA will be performed.
- PASI Score will be evaluated.
- BSA will be measured.
- DLQI questionnaire will be completed.
- I-NRS questionnaire will be completed.
- Measurement of vital signs (SBP/DBP and heart rate).
- Weight will be measured.

- CCTA will be performed.
- AEs will be recorded.
- Subjects will be instructed to return to the clinic in 2 weeks for Follow-up Visit 8 (or discharged from the study if terminated early).

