3.2.5 Follow-up (FU) Visit

3.2.5.1 Visit 8 (Week 17, Day 120 \pm 3 days)

A post-treatment Follow-up Visit will occur 14 \pm 3 days after completion of the treatment period. Subjects will report to the clinic in the morning where the following activities will be performed:

- Review of concomitant medications and supplements.
- Physical examination will be performed.
- Urine pregnancy test will be performed.
- Measurement of vital signs (SBP/DBP and heart rate).
- AEs will be recorded.
- Subjects will be discharged from the study.

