4.2 Inclusion Criteria

Subjects may be enrolled if the following criteria are met:

1. Stable/chronic plaque psoriasis with PASI score of ≥ 12 AND involving $\geq 10\%$ of the subject's BSA.
2. Males and Females ≥ 30 years of age at time of consent.
3. Females of childbearing age must use 2 forms of birth control.
4. BMI ≥ 30 kg/m².
5. LDL ≥ 100 mg/dL at Screening.
6. All females must have a negative serum pregnancy test result at Screening and a negative urine pregnancy test at Day 1 (Visit 1) prior to dosing.

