If a subject discontinues the study prior to completion, the date the subject is withdrawn and the reason for discontinuation will be recorded in the source documents and eCRF. Although a subject will not be obliged to give his/her reason for withdrawing prematurely, the Investigator will make a reasonable effort to obtain the reason while fully respecting the subject's rights.

All subjects who are randomized and treated (i.e., received any amount of study treatment) will be included in the safety analyses. Thus, every effort will be made to contact any subject who fails to attend any Follow-up appointments/contacts, to ensure that he/she is in satisfactory health. If a subject withdraws from the study as a result of meeting discontinuation criteria (Section 4.4) after the start of study treatment administration, reasonable efforts should be made to have the subject return for the early termination evaluations (Section 3.2.4). Any subject withdrawn due to a suspected study treatment-related AE should be followed until resolution or stabilization of the event.

If a subject becomes pregnant, study treatment will be discontinued immediately. The subject will be followed until delivery or other termination of pregnancy for outcome.

The Sponsor has the right to terminate this study, and the Investigator/Investigational Site has the right to close the site, at any time, although this should occur only after consultation among involved parties. The Investigator will notify the IRB in writing of a premature termination of a study or closure of Investigational Site and will send a copy of the notification to the Sponsor.

Events that may trigger premature termination of a study or closure of an Investigational Site include, but are not limited to, a new toxicity finding, a request to discontinue the trial from a regulatory authority, non-compliance with the protocol, GCP violations, slow recruitment/low enrollment, or change in development plans for the study treatment.

Enrollment of new subjects and dosing of ongoing subjects will be temporarily stopped based on the stopping criteria (See Section 12.2). The Investigator, Sponsor, and the Medical Monitor will discuss whether a lower dose or any additional treatment guidelines should be implemented, or if the trial should be permanently stopped. Any proposed changes to the protocol to address such findings will be submitted for review and approval by the IRB and FDA prior to re-starting the trial.

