5.10.2 Contraceptive Measures

The subject or their heterosexual partner (if applicable) should be surgically sterile (vasectomy, hysterectomy, bilateral tubal ligation [both tubes tied], or bilateral oophorectomy [both ovaries removed]). If not, and the female subject or partner is of childbearing potential (could become pregnant), the subject must agree to use highly effective contraception during heterosexual intercourse throughout the study period and for 90 days following last dose of study drug. Examples of a highly effective method of contraception include double barrier methods (e.g., use of a condom and spermicide along with [choose 1 of the following] a diaphragm; hormone-containing pill, injection or implant; or intrauterine device [IUD]). The male subject must not donate sperm while participating in this study and for 90 days after receiving the last dose of study drug.

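### The Screening instruction ends contraception at Visit 8 (Day 120), but Protocol 5.10.2 and 7.3.3 require 90 days after the last dose (about Day 168).

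*Protocol*

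**What the plan says.** The protocol gives the contraception period in four places.

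- **3.2.1.1 Screening Visit.** Eligible subjects are to be instructed on contraception "for the duration of the study (Screening through Follow-up Visit (Visit 8"). The bullet refers to Section 5.10.2 for methods.
- **5.10.2 Contraceptive Measures.** Where pregnancy is possible, each participant "must agree to use highly effective contraception during heterosexual intercourse throughout the study period and for 90 days following last dose of study drug". This covers female subjects and the female partners of male subjects.
- **7.3.3 Pregnancy.** A female of childbearing potential must agree to contraception during the study and "for 90 days after the last dose of study drug to be eligible for participation in the study". The section refers to 4.2 and 5.10.2.
- **4.2 Inclusion Criteria, criterion 3.** "Females of childbearing age must use 2 forms of birth control", with no period given.

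On what happens if a pregnancy occurs, 7.4.2.1 requires a report if the subject or partner "becomes pregnant during the study or within 30 days of discontinuing study medication". Section 4.4, where it deals with stopping study treatment for pregnancy, adds: "The subject will be followed until delivery or other termination of pregnancy for outcome". At the early termination visit (3.2.4.1) subjects who stop early are not called back for Visit 8; they are "or discharged from the study if terminated early". The SAP is silent on all of this.

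**The concern.** The Screening bullet is the instruction that site staff pass on to subjects, and it carries an explicit end point earlier than the rule it cites. A site that follows 3.2.1.1 literally gives a stop date that contradicts a condition of eligibility. Nothing later in the visit schedule corrects the message: the Visit 8 procedures in 3.2.5.1 include a urine pregnancy test and discharge, but no reminder that contraception must continue.

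What is at stake is an avoidable conception in a period that the protocol itself treats as needing protection, while some drug may still be present. A secondary matter is that such a conception could fall outside the pregnancy reporting window, so that no exposure form or outcome follow-up would be required.

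**Working it through.** There is no stated figure to reproduce. The check is day arithmetic on the visit schedule, followed by a look at the protocol's own concentration data.

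**Inputs**
- Last dose: Visit 6, Day 78 ± 3 (3.2.3.6).
- Last visit: Visit 8, Day 120 ± 3 (3.2.5.1).
- Contraception period: 90 days after the last dose (5.10.2, 7.3.3).
- Pregnancy reporting: during the study, or within 30 days of stopping drug (7.4.2.1).

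**Contraception stop dates**
- Under 3.2.1.1: Day 120, which is 120 − 78 = 42 days after the last dose.
- Under 5.10.2 and 7.3.3: 78 + 90 = Day 168.
- Difference: 168 − 120 = **48 days** (Days 121 to 168).
- Smallest difference with ± 3 days at both visits: (75 + 90) − 123 = 42 days.
- Largest difference: (81 + 90) − 117 = 54 days.
- Footnote 1 of Table 1 allows only ± 1 day for Weeks 1 to 15. With that at Visit 6 the range is (77 + 90) − 123 = 44 to (79 + 90) − 117 = 52 days.

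A subject who stops early has no Visit 8, so the Screening wording gives that subject no usable date. I put no figure on that case.

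**Reporting window (the optional point)**
- Completers: the 30-day limit falls on 78 + 30 = Day 108, before Visit 8. Visit 8 is at least 117 − 81 = 36 days after the last dose, so the end of the study is always the later limit. The part of the 90 days not covered is again 48 days nominally.
- Early terminators discharged within 30 days of the last dose: cover ends at day 30, leaving 90 − 30 = 60 days. This is a maximum; it shrinks if the early termination visit comes later than that.

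**Is drug still present?** Protocol 1.2 reports the earlier Phase 2 study in atherosclerosis, dosed on the same days (1, 8, 15, 22, 50, 78) at lower doses than proposed here.
- Peak after the last dose: 197 ug/mL.
- Mean on Day 78, before dosing and 78 − 50 = 28 days after the previous dose: 15.4 ug/mL, or 15.4/197 = 7.8% of that peak.
- Mean on Day 169: 2.47 ug/mL, or 2.47/197 = 1.3% of peak. By day count this is 169 − 78 = 91 days after the last dose; the section calls it 12 weeks.

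So measurable drug remained at about the end of a 90-day period, at a low level relative to peak.

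**The case against.** The best defence is that 3.2.1.1 is an incomplete restatement and not a rival rule. Section 5.10.2 has two parts, the study period and the 90 days. The Screening bullet gives the first and points to the section that holds the second, and it never says that contraception may stop at Visit 8. Section 7.3.3 secures agreement to 90 days from females of childbearing potential before entry, and criterion 3 is silent rather than contradictory. The consent form is not among the documents reviewed, so what subjects sign for cannot be checked.

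Part of this stands. A careful site can find the 90-day rule, and the Screening wording releases nobody from it. But the cross-reference does not remove the shorter period printed beside it.

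Three stronger readings are tempting, and the documents do not support them.

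- **That the 30-day reporting limit is an error.** A contraception period and a reporting period need not be equal, no text conflicts with 7.4.2.1, and 30 days matches the SAE window in 7.4.2. Section 4.4 requires follow-up to outcome but sets no longer window.
- **That a large share of the drug remains when reporting stops.** The stated half-life of 2 to 3 weeks, put into a simple exponential, gives 0.5^(28/14) = 25% to 0.5^(28/21) = 40% at 28 days. The observed ratio at 28 days was 7.8%, some three to five times lower. A serum ratio includes distribution and is not the total amount in the body, so the two are not strictly the same quantity, but the exponential percentages should not be relied on.
- **That reproductive harm is likely.** The protocol reports no drug-related toxicological findings (1.1) and no pregnancies in the earlier Phase 2 study.

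**Conclusion.** The Screening instruction in 3.2.1.1 is wrong as written: its stop date is nominally 48 days earlier than 5.10.2 and 7.3.3 require. The figure assumes a completer dosed at Visit 6 and seen at Visit 8. It does not depend on any pharmacokinetic assumption; the concentrations observed in the earlier study show only that the protected period is not an empty formality.

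The mismatch between the 90-day contraception period and the reporting window is an opportunity to collect rare exposure data, not a defect. The documents give no pregnancy rate, so I estimate no count. Severity is minor, and no efficacy or safety analysis changes.

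**What to change.** **Correct:**
- In 3.2.1.1, replace the stated period with *from Screening until 90 days after the last dose of study drug*.
- Add the same period to criterion 3 in 4.2, so that the reference from 7.3.3 leads to a stated duration.

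**Optional, in the same amendment:**
- In 7.4.2.1, extend reporting to pregnancies during the study or within 90 days after the last dose.
- At Visit 8 or the early termination visit, remind subjects to call the site about any pregnancy, their own or a partner's, in that period. No extra visit is needed.

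The cost is a short protocol amendment with IRB approval and matching consent and safety wording where needed. The optional part may also mean following a rare post-study pregnancy to its outcome.
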